### **Statistical Design and Power of Study**

All statistical analyses will use two-tail tests with the significance level set at 0.05, using version 9.4 of SAS software (SAS v9.4, Cary, NC). Statistical reports will emphasize our desire to characterize the evidence, in addition to reporting significance levels. Prior to final analyses, we will screen the data, consult with the overarching COBRE PI, project mentors and our COBRE admin core biostatistician as needed. Statistical assumptions will be tested, & appropriate data transformations or model adjustments will be used as needed. Our COBRE admin core biostatistician [name] has extensive experience with these methods and is equipped for supporting this study's needs.

### **Experimental Design:**

Fifty participants will be recruited in a rolling sample collection from the Greater Grand Forks area of North Dakota and Minnesota. A respondent driven rolling sampling method will be used for adults between the ages of 18-65 years of age. Ages have been specified as such due to the substantially changing metabolic profiles in children and older adults. We have proposed a first step cross-sectional baseline data collection process followed by a longitudinal intervention design in this exploratory study examining the effects of consuming traditional Indigenous chokeberry on metabolic, epigenetic and mental health markers where subjects will serve as their own control.

*Randomization Note:* It is considered almost unethical at this time to conduct double blind, placebo control studies with Indigenous subjects. There has been long-standing historical mistrust that Indigenous communities have with research. This is due to often being taken advantage of in the past by researchers, and even having been the subject of experimental studies that would have been considered illegal by today's IRB standards. The idea of 'tricking' somebody with a placebo agent is not a way to build trust with this population, so adjustments to the standard study design are imperative to build trust, research interest and capacity in Indigenous settings. By supporting Indigenous investigators to lead research with their own populations gives further opportunity for community trust building with institutional settings. This is consistent with the NIH's own 2019-2023 Strategic Plan for Tribal Health Research which helps define the research variables and goals for research in Indigenous communities. The project has been designed with the best possible rigor that is realistic in an American Indian participant setting with involvement of the American Indian community including an Elder to ensure involvement and success.

### **Sample Size, Power and Attrition:**

The proposed project aims to test the differences in gene expression, epigenetic (e.g. methylation) and metabolic endpoints (e.g. IL-6, 8-OHdG, lipids) between baseline and post 6 weeks of daily chokeberry consumption. Our sample will include fifty American Indian participants. With a sample of 50 and a conservative effect size as small as 0.4, we have a power of 79.2% with a two-sided paired test and level of significance at 0.05. We consulted the literature on the effects of our proposed chokeberry intervention on the metabolic outcome measures proposed in our study. The median effect size from these studies in the literature (significant findings) is 1.12, which is much higher than 0.4. Therefore, we expect to have a power higher than 79.2%. As to epigenetic endpoints, to the best of our knowledge, there is no study that has been published to

test chokeberry's effects on human IL-6 promoter CpG island methylation changes. Only a few cell culture studies have shown DNA methylation changes using anthocyanin rich fruits with reported effect size >0.4. Thus, we believe that we should have sufficient power to perform the proposed exploratory study with a sample of size 50. As American Indian populations (which are the basis for this study) have unique research needs and history, we consulted the literature to determine the average attrition rate of studies with the American Indian population. We were able to find literature specific to the reservation areas of North Dakota and used this information in our calculations.

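### The 79.2% power assumes 50 complete pairs, but 50 is the number recruited, so it contains none of the attrition the plan says it used

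*Combined protocol and SAP*

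**What the plan says.** The Experimental Design section sets the recruitment number: "Fifty participants will be recruited in a rolling sample collection". Participants act as their own controls, so each person who completes contributes one baseline/week-6 pair.

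The section on sample size, power and attrition uses the same number: "Our sample will include fifty American Indian participants". It then gives the plan's only power figure: "With a sample of 50 and a conservative effect size as small as 0.4, we have a power of 79.2" per cent, for a two-sided paired test at the 0.05 level. It concludes that "we should have sufficient power to perform the proposed exploratory study with a sample of size 50".

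On dropout, the section reports that "we consulted the literature to determine the average attrition rate of studies with the American Indian population". It adds that literature specific to North Dakota reservation areas was found and that the authors "used this information in our calculations". It gives no rate, no expected number of completers and no inflated recruitment target.

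The section also expects to do better than the stated power for metabolic outcomes: "The median effect size from these studies in the literature (significant findings) is 1.12", followed by "Therefore, we expect to have a power higher than 79.2" per cent.

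**The concern.** An attrition rate above zero must show up in one of two places. Either recruitment exceeds the number needed for analysis, or the power is computed on fewer people than are recruited. Here both numbers are 50, so the statement that attrition entered the calculations cannot be matched to anything shown.

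The planned analyses do not recover the loss. The paired t-test and Wilcoxon signed rank test under the Phase 2 aim need both measurements. The repeated-measures linear model under the Phase 1 aim supplies no week-6 value for someone who has left, and no method for missing data is described.

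The 79.2% is the only quantified support for the claim that 50 is enough. If it overstates the power at the planning effect, a reader cannot tell what power, or what detectable effect, the expected completers provide.

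**Working it through.** **Inputs.** n = 50, standardised effect d = 0.4, two-sided α = 0.05 and a paired test, all from the sample size section; 50 recruited, from the Experimental Design section. The plan does not define its effect size. I take d as the mean paired difference divided by the standard deviation of the differences, an assumption supported by the match below.

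**Formula.** For a paired t-test on n pairs, with t_c the 97.5th percentile of t on n − 1 degrees of freedom and noncentrality λ = d√n:

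power = P(T > t_c) + P(T < −t_c), where T is noncentral t with n − 1 degrees of freedom and noncentrality λ.

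**The plan's figure.** With n = 50, λ = 0.4 × √50 = 2.828 and t_c = 2.010. Power is 0.7918, which rounds to the stated 79.2%.

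**Could 79.2% already be a figure for fewer completers?**
- Exact t: 49 pairs give 0.7834 and 51 give 0.7999.
- Normal approximation, Φ(0.4√n − 1.96): 0.8074 (n = 50), 0.7996 (49), 0.7914 (48), 0.7830 (47). None rounds to 79.2%.
- One-sided t at n = 50: 0.874.

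Of these, only the exact two-sided paired t-test with 50 complete pairs gives 79.2%.

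**Effect of losing participants.** The documents give no rate, so the losses below are assumptions. The third column is power at d = 0.4. The fourth is the effect detectable with 80% power. The fifth is the true effect needed to keep power at 79.2%.

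| Assumed loss from 50 | Pairs | Power at 0.4 | Effect for 80% power | Effect for 79.2% power |
|---|---|---|---|---|
| None | 50 | 79.2% | 0.404 | 0.400 |
| 10% | 45 | 74.7% | 0.427 | 0.423 |
| 20% | 40 | 69.4% | 0.454 | 0.450 |
| 30% | 35 | 63.3% | 0.487 | 0.482 |

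For small losses, one dropout gives 78.3% and two give 77.5%, a fall of under 2 points. Power first drops below 75% at 5 losses (46 pairs 75.6%, 45 pairs 74.7%) and below 70% at 10 losses (41 pairs 70.5%, 40 pairs 69.4%).

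**If the true effect is larger.** At d = 0.5, power is 90.7% with 45 pairs, 86.9% with 40 and 82.0% with 35.

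**The case against.** No calculation is wrong: 79.2% is right for its inputs. The text does not say which calculation used the attrition rate, so 50 could be meant as analysed pairs, with the recruitment sentence loosely worded. The plan calls 0.4 conservative and expects larger effects. At the cited median of 1.12, even 35 pairs give power above 99.9%. The study is exploratory, and the size of any shortfall is unknown because every loss above is assumed.

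Much of this stands. The arithmetic is sound, the shortfall cannot be fixed from the documents, and one or two dropouts hardly matter. The plan already says that the 1.12 median comes from significant findings, and it treats epigenetic endpoints separately, so that material is at most a matter of tidier wording.

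It does not remove the point. Reading 50 as completers contradicts the statement that fifty will be recruited, has no larger enrolment target behind it, and would itself require a correction. Larger effects do not restore a figure stated at 0.4. The 1.12 median concerns metabolic outcomes. For IL-6 promoter methylation the plan knows of no human chokeberry study and cites only a few cell culture studies, so 0.4 remains the working value there.

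**Conclusion.** The concern holds. The stated power is the zero-attrition figure for all 50 recruits, in a section that says attrition was taken into account. At an effect of 0.4, any loss before week 6 brings power below 79.2%. The amount depends on a rate the plan does not disclose: under 2 points for one or two losses, and 4.5, 9.8 and 15.9 points at assumed losses of 10%, 20% and 30% (79.2 less 74.7, 69.4 and 63.3).

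This rests on the exact paired t-test, on the effect being standardised by the standard deviation of the differences, and on dropouts contributing no week-6 value. It concerns the accuracy of the stated figure, not whether the study can be done. It should be fixed, but it does not undermine the design.

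**What to change.** Keep recruitment at 50. In the sample size section, state the attrition rate already found and the expected number of completers, N_c = 50 × (1 − rate). Replace 79.2% with the power at an effect of 0.4 for N_c pairs, and add the effect detectable with 80% power at N_c. Update the figure in the sentence that expects higher power. Limiting that sentence explicitly to metabolic outcomes would make it clearer, but this is optional.

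If 50 was meant as the number of completers, the recruitment sentence in the Experimental Design section has to be corrected to the larger target instead.

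With recruitment kept at 50, the cost is a few words and a short recalculation from a rate the plan says it holds. Sample size and analysis do not change. The drawback is a less favourable stated power.

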**Phase 1 Specific Aim:**

For this portion of the statistical analysis, an established method for analyzing epigenetic differences at time points will be utilized. It must be noted that due to the small sample size in this exploratory study design the following statistical procedures will be employed. Normality of continuous variables will be assessed. For non-normal data, appropriate transformations (e.g. log transformations) and/or non-parametric tests will be applied for further statistical analysis. Back-transformations will be used for the interpretation of the final results. Correlation analyses will be performed by the Pearson's correlation test (or Spearman correlation for non-normal data). A general linear model with repeated measurements will be used to assess differences between baseline and post 6 weeks of daily chokeberry consumption with confounding variables adjusted. If multiple epigenetic markers are tested, family-wise Type I error rate will be controlled with standard methods (e.g. Bonferroni, False Discovery Rate method). The Student's t-test for independent samples will be performed to assess gender differences. A p-value of <0.05 will be considered as statistically significant for all statistical assessments in this research project. Future research steps could include a more complex mixed model design where interaction and mediation effects can be tested with a larger sample size pending the outcomes noted here.

[figure not shown]

Figure 2. Three step research strategy

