**Phase 2 Specific Aim:**

Baseline and post 6 weeks of chokeberry:

All statistical analyses associated with this cross-sectional portion of the study will be performed using a statistical analysis system software (SAS v9.4, Carry, NC). To investigate the association between the cross-sectional measures (i.e., adverse childhood experiences, historical trauma, resiliency, presence of anxiety and depression, metabolic markers (i.e., 8-OHdG, IL-6, lipids, glucose, CRP, blood pressure)) and baseline epigenetic measures, simple and multivariable linear regression models will be run. Adjustment will be made for the confounders of interest (i.e., smoking status, BMI, physical activity levels, presence of comorbidities, anti-depressant and/or anti-anxiety medication use, supplement use, nutritional intake, age and gender). For the metabolic end points, the values will be expressed as means ± SD. Statistical tests will be performed using the same commercial software package (SAS v9.4, Carry, NC) as described above. The Kolmogorov–Smirnov test will be applied to determine whether the continuous variables are normally distributed. For within group comparison vs baseline, variables showing normal distributions will be evaluated using the paired t test, while variables showing non-normal distributions will be evaluated using the Wilcoxon signed rank test. Our null hypothesis is that chokeberries will not have an effect on gene expression, metabolic markers or mental health status in Great Plains Indian subjects. As noted previously, a p-value of <0.05 will be considered as

statistically significant for all statistical assessments in this research project. Again, future research steps could include a more complex mixed model design where interaction and mediation effects can be tested with a larger sample size pending the outcomes noted here. See *Figure 2*, above for a summary of the study steps.

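### Does the unspecified covariate adjustment in the Phase 1 repeated-measures model detach its time test from the change the study was powered on?

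*Combined protocol and SAP*

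**What the plan says.** Under Sample Size, Power and Attrition, the Combined protocol and SAP states "Our sample will include fifty American Indian participants" and, for an effect size of 0.4 at the 0.05 level, "we have a power of 79.2% with a two-sided paired test". Experimental Design describes a single-arm before-after study "where subjects will serve as their own control".

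For the epigenetic comparison, Phase 1 Specific Aim says "A general linear model with repeated measurements will be used". The target of that model is given as "differences between baseline and post 6 weeks of daily chokeberry consumption with confounding variables adjusted". The section gives no covariate list, coding, covariate-by-time terms, time contrast or SAS procedure. The same section leaves to future research "a more complex mixed model design where interaction and mediation effects can be tested with a larger sample size", and Phase 2 Specific Aim repeats that deferral.

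The only confounder list is in Phase 2 Specific Aim: "Adjustment will be made for the confounders of interest (i.e., smoking status, BMI, physical activity levels", then comorbidities and psychiatric medication, and finally "supplement use, nutritional intake, age and gender". These nine items belong to the regressions on baseline epigenetic measures, not to the Phase 1 before-after model. Phase 2 also provides a paired t test or signed rank test for comparison with baseline. That text follows the metabolic endpoints, although the null hypothesis stated after it also names gene expression. Statistical Design and Power of Study says that a biostatistician will be consulted as needed before final analyses and that models may be adjusted.

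**The concern.** The power statement and the Phase 1 analysis are not visibly the same test. A covariate fixed over six weeks cannot confound a within-person change, so it is unclear what the adjustment is for. The form of the model also matters. A classical multivariate repeated-measures routine regresses each time point on the covariates, which crosses every covariate with time even when no interaction was requested. If age or BMI then enters on its raw scale, the line labelled time tests the change in a person of age zero or BMI zero.

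If that line were reported as the chokeberry effect, a real average change could be missed. If change varied with age, a change could be declared when the average change is zero. The 79.2% power would describe neither case.

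**Working it through.** **Inputs.** From the plan: n = 50, effect size d = 0.4, two-sided alpha 0.05, ages 18-65. Assumed, because the plan does not give them: age uniform on 18-65 (mean 41.5, variance 47²/12 = 184.08, SD 13.57); BMI mean 30, SD 6; any correlation between age and change.

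**1. The plan's own figure.** Paired t test, noncentrality 0.4 × √50 = 2.828 on 49 df: power 79.18%. The stated 79.2% is reproduced.

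**2. Main effects only.** A baseline covariate has the same value at both visits, so it cancels from the within-person difference. With complete pairs the time test is the paired test.

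**3. Crossed with time.** With two time points, the time test is the intercept test in a regression of change on the covariates. For one covariate, the variance of the intercept relative to that of the mean change is

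1 + n·x̄² / ((n − 1)·s²).

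- Age, uncentred: 1 + 50 × 41.5² / (49 × 184.08) = 10.55, so the standard error is multiplied by √10.55 = 3.25. Noncentrality is 2.828 / 3.25 = 0.87 on 48 df; power 13.7%. With age assumed to have mean 40 and SD 12, power is 12.4%.
- Age plus BMI, uncentred and uncorrelated: 1 + (50/49) × (41.5²/184.08 + 30²/36) = 36.06, multiplier 6.0, power 7.5%. For BMI mean 28-30 and SD 5-8, power is 7-9%.
- Mean-centred: x̄ = 0, so the ratio is 1 and only degrees of freedom are lost. Power is 79.1% with one covariate and 78.8% with nine, if they explain none of the change.

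**4. False positives.** Suppose the mean change is zero and change correlates 0.3 with age. In SD units of change, the expected change at age zero is −0.3 × 41.5 / 13.57 = −0.92. Its standard error is 3.25 × √(1 − 0.09) / √50 = 0.44, a ratio of about 2.1. Simulation gives 54% rejection for uncentred age, about 6% for centred age and 5% for the paired test. At correlations of 0.1 and 0.2 the uncentred test rejects in 10% and 26% of trials.

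**5. One simulated data set, estimate of the time effect (SE).**

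| Model | Estimate (SE) |
|---|---|
| Paired difference | 0.577 (0.140) |
| Age as main effect, centred or not | 0.577 (0.140) |
| Age × time, centred | 0.577 (0.140) |
| Age × time, uncentred | 0.960 (0.411) |

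**6. Making the paired test primary.** Suppose chokeberry has no effect, but a covariate that can move over six weeks shifts by 0.5 SD of its own change and correlates 0.3 with the change in outcome. The outcome then drifts by 0.5 × 0.3 = 0.15 SD. In simulation the paired test rejects in about 18% of trials and a model adjusted for the covariate's change score in about 5%. If the change score is itself mean-centred, the intercept is again the raw mean change and rejection is 20-21%.

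**The case for a change.** The best case for amending the plan is that clarification is nearly free. Deferring tests of interactions as hypotheses does not fix the form of the fitted model, because a multivariate repeated-measures fit brings in covariate-by-time terms by construction. An analyst could follow Phase 1 to the letter and report the wrong line. The plan applies p < 0.05 to all its assessments, so the exploratory label does not remove the need to know what is being estimated. A few lines making the paired change primary and centring the covariates would close the gap.

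Part of this stands. The Phase 1 model is under-described, the deferral of interactions points to main effects without settling the matter, and the arithmetic above is correct for the fit it describes.

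The rest does not carry. The low power and high false-positive figures belong to a coding choice the plan does not make, with covariates the plan does not assign to this model and distributions it does not give. Nor is the proposed remedy a clear gain. With no control group, shifts in diet, activity or supplement use are a real rival explanation, and an unadjusted primary test gives up the one analysis that could address them (step 6). A blanket instruction to centre covariates would also cancel the adjustment if it were applied to change scores.

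**Conclusion.** The concern does not hold as a reason to change the plan. Harm needs three things together: covariates crossed with time, left on their raw scale, and the raw time line read as the average change. The plan states none of them. Under the ordinary choices, main effects with complete pairs or centred baseline covariates, the Phase 1 time test is the mean within-person change. Its power is then between 78.8% (nine centred covariates explaining none of the change) and the stated 79.2%.

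The drop to about 14% or 7% power, and the 54% rejection rate at zero mean change, rest on the assumed age and BMI distributions and an assumed 0.3 correlation. They show what a careless fit could do, not what this plan prescribes. What remains is a gap in detail of the kind a biostatistician settles when fitting the model, and the plan provides for consulting one as needed before the final analyses. Whether the paired or the adjusted analysis should lead is a fair trade-off for the sponsor.

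### The Phase 1 Specific Aim promises family-wise error control for multiple epigenetic markers but lists a False Discovery Rate method as a way to deliver it, which in general it does not

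*Combined protocol and SAP*

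**What the plan says.** The multiplicity rule is one sentence in the Phase 1 Specific Aim section of the combined protocol and SAP: "If multiple epigenetic markers are tested, family-wise Type I error rate will be controlled with standard methods (e.g. Bonferroni, False Discovery Rate method"). It is conditional, it names one error rate, and it offers two example methods without choosing between them. It names no particular FDR procedure and no FDR level.

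The same section adds: "A p-value of <0.05 will be considered as statistically significant for all statistical assessments in this research project". The Statistical Design and Power of Study section likewise states: "All statistical analyses will use two-tail tests with the significance level set at 0.05". Neither says whether 0.05 applies to raw or adjusted p-values where a correction is used.

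The one specific epigenetic endpoint in the documents is in Sample Size, Power and Attrition, which refers to "human IL-6 promoter CpG island methylation changes". That could be analysed as one summary value or as several CpG sites. The documents do not say how many markers there will be.

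**The concern.** Family-wise error is the chance of at least one false positive among the markers. The false discovery rate is the expected share of false positives among the markers declared significant. Bonferroni controls the first. BH, the usual FDR method, controls the second. The sentence treats them as two routes to the same guarantee.

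Two things follow. First, an analyst could apply BH and, with the plan's authority, report family-wise control that the method does not give. Second, because the choice is open, two analysts following the plan could report different significant markers from the same data, both under the same claim.

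**Working it through.** **Inputs from the documents.** n = 50, standardised paired effect 0.4 and power 79.2% (Sample Size, Power and Attrition); two-sided alpha 0.05 (Statistical Design and Power of Study).

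**Assumptions, because the documents are silent.** BH at 5% stands for the FDR method. Marker count, share of markers changed and correlation between markers are varied.

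**1. The plan's own figure.** For a paired t test with 49 degrees of freedom and noncentrality 0.4 × √50 = 2.828, two-sided power at 0.05 is 79.18%. This reproduces 79.2%. It is the power of one unadjusted test.

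**2. How the two rates relate.** Let V be the number of false rejections and R the number of all rejections. Family-wise error = P(V ≥ 1); FDR = E[V / max(R, 1)]. The ratio never exceeds 1 and is zero when V = 0, so FDR ≤ family-wise error. Controlling family-wise error therefore controls FDR, but not the reverse. The two are equal when no marker changes.

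**3. A case that can be done by hand.** Take 10 independent markers, 5 of them changed so strongly that they are always rejected.

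- BH then tests the smallest of the 5 null p-values against 0.05 × 6/10 = 0.03. Family-wise error is about 1 − 0.97⁵ = 14.1%. Simulation at effect 1.12 gives 14.1%.
- Holm tests it against 0.05/5 = 0.01, giving about 1 − 0.99⁵ = 4.9%.
- If only one marker is unchanged, BH rejects it only when its p-value is at most 0.05, so there is no excess. This covers two markers with one changed, and 10 with 9 changed.

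**4. The plan's effect size of 0.4.** These are simulated family-wise error rates from two-sided paired t tests at n = 50. Runs used 40,000 to 200,000 trials; at 100,000 trials and a rate of 5% the standard error is √(0.05 × 0.95/100,000) = 0.07 percentage points.

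| Markers (changed) | Correlation | BH | Holm |
|---|---|---|---|
| 2 (1) | 0 | 4.5% | 4.3% |
| 3 (1) | 0 | 5.8% | 4.4% |
| 3 (2) | 0 | 4.2% | 3.5% |
| 4 (2) | 0 | 6.2% | 3.9% |
| 6 (3) | 0 | 7.6% | 3.6% |
| 10 (5) | 0 | 10.7% | 3.4% |
| 10 (5) | 0.5 | 7.7% | 3.0% |
| 10 (5) | 0.7 | 6.1% | 2.7% |
| 10 (5) | 0.9 | 4.1% | not above 5% |
| 10 (1) | 0 | about 7% | not above 5% |
| 10 (9) | 0 | 4.0% | not above 5% |
| 2 to 10 (none) | 0 | 5.0–5.1% | 4.9–5.0% |

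Bonferroni is never less strict than a 5% family-wise limit and lies at or below Holm in every row.

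**5. How often Bonferroni and BH list different markers** (effect 0.4).

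- Half changed, independent: 2% of trials with 2 markers, 16% with 4, 33% with 6, 61% with 10.
- Half changed, correlation 0.7: about 2%, 15%, 28% and 49%.
- 10 independent markers: 3% with 1 changed, 61% with 5, 92% with 9.

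**The case against.** The strongest reply is that little may turn on this. The sentence opens "If multiple epigenetic markers are tested", and if methylation is analysed as one summary value it never applies. If several CpG sites are tested they are probably correlated, and the excess then shrinks: at correlation 0.7 with half changed, BH gives 4.8% for 4 markers and 5.3% for 6. The share of markers changed matters as much, and it too is unknown. The study is exploratory, for which FDR control is a reasonable target.

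All of this stands, and it limits the weight of the point. It does not make the sentence right. The plan chose to promise that the "family-wise Type I error rate will be controlled with standard methods", and no other section redefines that term or confines the FDR method to a setting where the promise would hold. High correlation also leaves the open choice in place: at 0.7 the two listed methods still disagree in about 15% to 49% of trials with 4 to 10 markers, half of them changed.

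A reader might infer that the study's epigenetic false-positive rate will be about 11%. The documents do not support that. The figure needs 10 independent markers, half of them changed, and the use of BH; none of these is stated. A reader might also infer that FDR control is the wrong choice here, or that the Phase 2 metabolic tests share this fault. Neither follows: FDR control is acceptable if named as such, and the Phase 2 tests carry no family-wise promise, so their multiplicity is a separate matter.

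**Conclusion.** The statement is wrong as written, and the correction is minor. BH and similar FDR procedures do not in general deliver the family-wise control that the Phase 1 Specific Aim promises.

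The shortfall cannot be fixed at one number. At n = 50 and effect 0.4, with up to 10 markers and some changed, BH family-wise error lies between about 4% (most markers changed, or correlation near 0.9) and about 11% (10 independent markers, half changed). It would be larger with stronger effects, as the hand calculation shows. With two markers, or if no marker changes, there is no material excess and only the label is wrong.

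The more practical consequence is the unfixed choice of method, which can change the list of significant markers. How often it does so also depends on the unstated share changed and correlation.

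**What to change.** In the Phase 1 Specific Aim, before analysis, replace the two examples by one method with its correct error rate:

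- keep the family-wise claim and name Bonferroni, which the plan already lists, or Holm, which has more power at no cost in family-wise control; or
- name Benjamini-Hochberg, describe it as false-discovery-rate control at 5%, and drop the family-wise claim.

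In either case state that, for these markers, 0.05 applies to the adjusted p-values.

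The drafting cost is about two sentences; design and sample size do not change. The statistical cost of keeping family-wise control is power. The table gives average power per changed marker at effect 0.4, for independent markers with half changed. The Bonferroni values are those of the paired t test above at two-sided level 0.05/m for m markers.

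| Markers | BH | Holm | Bonferroni |
|---|---|---|---|
| 4 | 67.2% | 62.4% | 59.5% |
| 6 | 65.9% | 56.9% | 53.6% |
| 10 | 64.7% | 49.6% | 46.3% |

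All are below the plan's 79.2%, which holds for a single unadjusted test. The cost of choosing BH is that the report may no longer claim family-wise control.

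### The gender comparison uses an equal-variance Student t-test, whose error rate is wrong if men and women differ in both number and variance; Welch's test avoids this at little cost

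*Combined protocol and SAP*

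**What the plan says.** The Phase 1 Specific Aim section gives the gender comparison one sentence: Student's "t-test for independent samples will be performed to assess gender differences". It does not say which markers are compared, or whether the values are from baseline, week 6 or the change between them.

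The effect of the intervention has its own analysis in the same section: "A general linear model with repeated measurements will be used to assess differences between baseline and post 6 weeks of daily chokeberry consumption", with adjustment for confounders. Interactions are left to a later, more complex model, "where interaction and mediation effects can be tested with a larger sample size pending the outcomes noted here".

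On recruitment, Experimental Design says only this: "A respondent driven rolling sampling method will be used for adults between the ages of 18-65 years of age". No gender split or quota is given. The total is fixed in Sample Size, Power and Attrition: "Our sample will include fifty American Indian participants".

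On assumptions, Statistical Design and Power of Study promises: "Statistical assumptions will be tested, & appropriate data transformations or model adjustments will be used as needed". The Phase 1 section spells out a check and a remedy for non-normality. Neither section names equal variance or Welch's test.

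**The concern.** Student's test pools the two sample variances. When the groups differ in size, the pooled value is weighted toward the larger group. If the smaller group is the more variable one, the standard error is too small and false positives rise. If the larger group is the more variable one, the standard error is too large and the test becomes too cautious. With 50 participants and no control on the gender split, neither direction can be excluded in advance.

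At stake is the reliability of any p-value reported for gender. Because variable and time point are open, it is also unclear which question that p-value would answer.

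**Working it through.** **Inputs from the documents.** Alpha is 0.05 two-sided ("All statistical analyses will use two-tail tests with the significance level set at 0.05"), and the total is 50.

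**Assumed inputs.** The documents give neither the gender split nor the SD by gender. I take splits of 25/25, 30/20, 35/15 and 40/10, SD ratios between 0.5 and 2, and normal data.

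**Step 1. The plan's own figure.** The plan states: "With a sample of 50 and a conservative effect size as small as 0.4, we have a power of 79.2% with a two-sided paired test". With 49 degrees of freedom and noncentrality 0.4 × √50 = 2.83, the noncentral t gives 79.18%, which agrees. This figure concerns the paired comparison. The plan states no power for the gender comparison.

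**Step 2. Why Student's test fails at 35/15.** The true variance of the difference in means is s₁²/35 + s₂²/15. Student's test estimates it as [(34 s₁² + 14 s₂²)/48] × (1/35 + 1/15). The rejection rate is approximately 2 × [1 − Φ(1.96/√R)], where R is true variance over pooled variance.

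- Equal SDs: R = 1, so the rate is 5%.
- Smaller group 1.5 times: true 1/35 + 2.25/15 = 0.1786; pooled (34 + 31.5)/48 × 0.0952 = 0.1300; R = 1.374; rate about 9.5%.
- Smaller group 2 times: true 1/35 + 4/15 = 0.2952; pooled (34 + 56)/48 × 0.0952 = 0.1786; R = 1.653; rate about 12.7%.
- Larger group 1.5 times: true 2.25/35 + 1/15 = 0.1310; pooled (76.5 + 14)/48 × 0.0952 = 0.1796; R = 0.729; rate about 2.2%.

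**Step 3. Simulation** (400,000 replicates per setting, no true difference). Type I error of Student's test:

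| Split | Equal SDs | Smaller group 1.5× SD | Smaller group 2× SD | Smaller group 0.5× SD |
|---|---|---|---|---|
| 25/25 | 5.0% | 5.1% | 5.2% | 5.2% |
| 30/20 | 5.0% | 7.0% | 8.5% | 2.8% |
| 35/15 | 5.0% | about 9.5% | 12.8% | 1.4% |
| 40/10 | 5.0% | 12.2% | 18.3% | 0.5% |

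At 35/15 with the larger group at 1.5 times the SD, the rate is 2.3%. Welch's test lies between 4.9% and 5.2% in every setting. The first column shows that imbalance alone is harmless, and the first row shows that unequal variances in equal groups are nearly so.

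**Step 4. Testing the variances first.** At 35/15 with 1.5 times the SD in the smaller group, an F test detects the inequality only about 46% of the time. Choosing Student or Welch from its result gives about 6.9%, against about 9.5% for Student alone and 5.1% for Welch alone.

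**Step 5. What a gender test on change could detect.** For a gender difference of 0.4 SD of the change score, the noncentrality is 0.4/√(1/n₁ + 1/n₂).

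| Split | Noncentrality | Power at 0.4 SD | Difference detectable at 80% power |
|---|---|---|---|
| 25/25 | 1.41 | 28% | 0.81 SD |
| 30/20 | 1.39 | 27% | 0.83 SD |
| 35/15 | 1.30 | 25% | 0.88 SD |
| 40/10 | 1.13 | 20% | 1.01 SD |

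**The case against.** **The plan already promises to test assumptions and adjust.** This stands in part. A careful analyst could switch to Welch's test under that promise, so the Student figures above describe the test as named, not necessarily the test as finally run. But the promise does not mention variance, and at these group sizes a preliminary test misses the problem about half the time (step 4).

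**The inputs are assumed.** This stands. The documents do not show that the genders will be unequal in number or in spread. The error rates are conditional, and no departure is shown for this trial.

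**Two stronger readings are tempting, and neither is supported.** The first is that gender imbalance by itself spoils the test. It does not: with equal SDs the error rate is 5.0% at every split tried. The second is that the plan will report a pre-existing gender difference as a difference in response. If both genders changed equally but differed throughout by an assumed 0.5 SD, a test on week-6 values would be significant in about 41% of trials at 25/25 and 36% at 35/15, whereas a test on change would stay near 5%. But the plan never says that the gender test is run at week 6 or read as response. A baseline gender comparison would be legitimate, and a week-6 test that finds a real difference in level is not in error. Those percentages describe a possible misuse.

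**A gender test on change is the kind of interaction that the plan defers.** This stands too. Such a test belongs here only as an exploratory specification.

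**Conclusion.** The point holds in a limited form. The plan names an equal-variance test where the conditions that would make it safe, equal group sizes or equal variances, are neither fixed nor known. If both fail, the distortion can run either way: at 35/15, from 2.3% to 12.8% across SD ratios of 1.5 in the larger group to 2 in the smaller. This rests on assumed splits, assumed SD ratios and normal data. The missing variable and time point are a gap in specification, not evidence of a wrong conclusion. The main pre-post analyses are unaffected. I class this as a cheap improvement.

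**What to change.** Replace the sentence on gender in the Phase 1 Specific Aim section with wording such as: *Gender differences will be tested with the Welch t-test, with the transformation or non-parametric route above for non-normal data. The variables and time point will be stated. Baseline gender differences will be reported as such. Any statement about gender differences in response will be based on within-person change (week 6 minus baseline) and labelled exploratory.* The report should give the low power from step 5 beside any such statement.

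The cost is a few sentences and, if the variances are in fact equal, a little power. For a 0.8 SD difference there is practically no loss at 25/25 (79.2% for both tests). At 35/15 the loss is about 1.5 points (71.8% to 70.3%), and at 40/10 about 4 points (60.4% to 56.1%).
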